4. Determine the efficacy of four doses of VGX-3100 , alone or in combination with imiquimod, as measured by histologic regression of vulvar HSIL to normal tissue	4. Proportion of subjects with no evidence of vulvar HSIL, no evidence of LSIL (VIN1), and no evidence of condyloma on histology (i.e. biopsies or excisional treatment) at the Week 48 visit
5. Determine the efficacy of four doses of VGX-3100 , alone or in combination with imiquimod, as measured by non-progression of vulvar HSIL to vulvar cancer as determined by histology	5. Proportion of subjects with no progression  of vulvar HSIL to vulvar cancer from baseline to Week 48 visit

 A treatment responder for the primary endpoint is defined as a subject with no histologic evidence of vulvar HSIL and no evidence of HPV-16 or HPV-18 in vulvar tissue at evaluation and who did not receive any non-study related treatment for vulvar HSIL. A treatment non-responder is defined as a subject with histologic evidence of vulvar HSIL or vulvar carcinoma at evaluation, or a subject with evidence of HPV-16/18 in vulvar tissue at evaluation, or a subject who received non-study related treatment for vulvar HSIL.

 Clearance of HPV-16 or HPV-18 is defined as being undetectable by PCR assay.

 Progression is defined as advancement to carcinoma by histology according to the Pathology Adjudication Committee.

6. Determine the efficacy of VGX-3100, alone or in combination with imiquimod, as measured by reduction in the surface area of qualifying vulvar lesion(s)
	
6. Percent reduction in the cumulative surface area of the acetowhite vulvar lesion(s) as determined by the quantitative analysis of standardized pre-biopsy photographic imaging of qualifying lesion(s) at Week 48 compared to baseline. Results will be classified as: no clinically significant lesion resolution (reduction in lesion area of 0-25%), partial lesion area resolution (>25% and <100% reduction) and complete lesion resolution (no visible lesion).

7. Describe the cellular immune response to VGX-3100, administered alone or in combination with imiquimod, post dose 4
	
7. Flow Cytometry response magnitudes at baseline and Week 27 visits

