
8. Determine the efficacy of four doses of VGX-3100 alone or in combination with imiquimod with respect to histopathologic regression of vulvar HSIL or virologic clearance of HPV-16/18 in vulvar tissue
	
8. Proportion of subjects with no histologic evidence of vulvar HSIL or no evidence of HPV-16/18 at Week 48 in vulvar tissue samples (i.e. collected via biopsy or excisional treatment)

 A qualifying lesion is defined as a vulvar lesion which is confirmed to be HPV-16 and/or HPV-18 positive and have histologically confirmed vulvar HSIL by the PAC at screening.

 Baseline photographic imaging is defined as photographs obtained at Day 0 prior to the first study dose. Digital photos will be analyzed with a computer program to calculate the total lesion size in cm^2.

Exploratory Objectives	Associated Exploratory Endpoints
1. Describe the efficacy of VGX-3100, administered alone or in combination with imiquimod, at Week 74 and/or Week 96 as measured by reduction in the surface area of the qualifying  vulvar lesion(s), in subjects who did not have complete lesion resolution at Week 48	1. Percent reduction in the cumulative surface area of the acetowhite vulvar lesion(s) as determined by the quantitative analysis of standardized pre-biopsy photographic imaging of qualifying lesion(s) at Week 74 and/or Week 96 compared to baseline  . Results will be classified as: no clinically significant lesion resolution (reduction in lesion area of 0-25%), partial lesion area resolution (>25% and <100% reduction) and complete lesion resolution (no visible lesion).
2. Describe the long term efficacy of VGX-3100, alone or in combination with prior imiquimod, as measured by histologic regression of vulvar HSIL	2. Proportion of subjects with no evidence of vulvar HSIL on histology (i.e. biopsies or excisional treatment) at Week 74 for subjects who receive 5 doses of VGX-3100 and at Week 96 for subjects who receive 6 doses of VGX-3100
3. Describe the long term efficacy of VGX-3100, alone or in combination with prior imiquimod, as measured by virologic clearance of HPV-16/18	3. Proportion of subjects with no evidence of HPV-16/18 in vulvar tissue samples at Week 74 and/or Week 96.

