## 2.2 SECONDARY OBJECTIVES AND ASSOCIATED ENDPOINTS

Secondary Objectives	Associated Secondary Endpoints
1. Evaluate the safety and tolerability of VGX-3100 delivered IM followed by EP with CELLECTRA™ 2000, alone or in combination with imiquimod	1a. Local and systemic events for 7 days following each dose as noted in the Participant Diary. 1b. All adverse events including SAEs, AESI's, SUSARs, UADEs, and other unexpected AEs for the duration of the study (through Week 100 visit) 
2. Determine the efficacy of four doses of VGX-3100, alone or in combination with imiquimod, as measured by histologic regression of vulvar HSIL	2. Proportion of subjects with no evidence of vulvar HSIL  on histology (i.e. biopsies or excisional treatment) at Week 48 visit
3. Determine the efficacy of four doses of VGX-3100, alone or in combination with imiquimod, as measured by virologic clearance of HPV-16/18 in vulvar tissue	3. Proportion of subjects with no evidence of HPV-16/18  in vulvar tissue samples at Week 48 visit
4. Determine the efficacy of VGX-3100 , alone or in combination with imiquimod, as measured by histologic regression of vulvar HSIL to normal tissue	4. Proportion of subjects with no evidence of vulvar HSIL, no evidence of vulvar LSIL (VIN1), and no evidence of condyloma on histology (i.e. biopsies or excisional treatment) at the Week 48 visit
5. Determine the efficacy of four doses of VGX-3100 , alone or in combination with imiquimod, as measured by non-progression of vulvar HSIL to vulvar cancer as determined by histology	5. Proportion of subjects with no progression  of vulvar HSIL to vulvar cancer from baseline to Week 48 visit
6. Determine the efficacy of VGX-3100, alone or in combination with imiquimod, as measured by reduction in the surface area of the qualifying  vulvar lesion(s)	6. Percent reduction in the cumulative surface area of the acetowhite vulvar lesion(s) as determined by the quantitative analysis of standardized pre-biopsy photographic imaging of the qualifying lesion (s) at Week 48 compared to baseline  . Results will be classified as: no clinically significant lesion resolution (reduction in lesion size of 0-25%), partial lesion area resolution (>25% and <100% reduction), and complete lesion resolution (no visible lesion).

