## 2.3 EXPLORATORY OBJECTIVES AND ASSOCIATED ENDPOINTS

Exploratory Objectives	Associated Exploratory Endpoints
1. Describe the efficacy of VGX-3100, administered alone or in combination with imiquimod, at Week 74 and/or Week 96 as measured by reduction in the surface area of the qualifying  vulvar lesion(s), in subjects without a complete resolution at Week 48	1. Percent reduction in the cumulative surface area of the acetowhite vulvar lesion(s) as determined by the quantitative analysis of standardized pre-biopsy photographic imaging of the qualifying lesion (s) at Week 74 and/or Week 96 compared to baseline  . Results will be classified as: no clinically significant lesion resolution (reduction in lesion area of 0-25%), partial lesion area resolution (>25% and <100% reduction), and complete lesion resolution (no visible lesion).
2. Describe the long term efficacy of VGX-3100, alone or in combination with prior imiquimod, as measured by histologic regression of vulvar HSIL	2. Proportion of subjects with no evidence of vulvar HSIL on histology (i.e. biopsies or excisional treatment) at Week 74 for subjects who receive 5 doses of VGX-3100 and at Week 96 for subjects who receive 6 doses of VGX-3100.
3. Describe the long term efficacy of VGX-3100, alone or in combination with prior imiquimod, as measured by virologic clearance of HPV-16/18	3. Proportion of subjects with no evidence of HPV-16/18 in vulvar tissue samples at Week 74 and/or Week 96.
4. Evaluate tissue immune responses to VGX-3100, and VGX-3100 with imiquimod, as measured in vulvar tissue samples	4. Assessment of pro-inflammatory and immunosuppressive elements in tissue 
5. Describe virologic clearance of HPV-16/18 from non-vulvar anatomic locations	5. Proportion of subjects who have cleared HPV-16/18 on specimens from non-vulvar anatomic locations without surgical intervention (inclusive of cervix, oropharynx, vagina and intra-anus) at Week 48 compared to baseline
6. Describe association of microRNA (miRNA) profile, previous vulvoscopy, and HPV testing results with Week 48 histologic regression	6. Vulvoscopy, HPV test results (vulvar swab and vulvar tissue) and miRNA profile (Day 0, Week 15 and 48) in conjunction with histologic regression of vulvar HSIL at Week 48 visit

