If after evaluation of the biopsy tissue HSIL remains, but there is a reduction in lesion size or no increase in lesion size from baseline ([Figure 2](#), Subgroups C or D), the Investigator has the option to give the subject a 5th dose of VGX-3100 at Week 52, and the subject will continue on study with vulvoscopy and biopsy at Week 74. Alternatively, the Investigator may choose to treat the subject with surgical or standard treatment, and the subject will continue on study without further biopsy.

The decision process following results of the Week 74 biopsy for subjects who completed this visit prior to Amendment 5.0 are described in [Figure 3 \(Appendix B\)](#) for the original study design. The evaluation process following results of the Week 74 biopsy under Amendment 5.0 are described in [Figure 3a](#) and are as follows: At Week 74, the subject will undergo repeat vulvar punch biopsy/biopsies of the same lesion as at study start Investigator(see [Table 2](#)). If, after evaluation of Week 74 biopsy tissue by the PAC, there is no evidence of HSIL (Subgroups A or B), the Investigator will use their clinical judgment regarding follow-up care of the subject (not part of study activities).

If, after evaluation of the biopsy tissue HSIL remains, but there is a reduction in the qualifying lesion(s) size or no change in lesion size from baseline (Subgroups C or D), the subject will receive further standard of care treatment (not part of study activities) per the Investigator's judgment.

The decision process for subjects who are beyond Week 78 at the time of IRB approval of Amendment 5.0 can be found in [Appendix C](#). These subjects will complete the study at their next scheduled visit as outlined in [Table 1](#). Subjects must sign the IRB-approved informed consent document for Amendment 5.0 prior to the initiation of procedures for their final study visit.

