### 3.2.2 DEFINITION OF RESPONDER AND NON-RESPONDER FOR THE SECONDARY AND EXPLORATORY ENDPOINTS

Table 4: Definition of Responder and Non-responder for HSIL Regression Endpoint	
Responder	Non-Responder
Subject with no histologic evidence of vulvar HSIL AND Subject who did not receive any non-study related treatment for vulvar HSIL	Subject with histologic evidence of vulvar HSIL or vulvar carcinoma at evaluation OR Subject who received non-study related treatment for vulvar HSIL

Table 5: Definition of Responder and Non-responder for Viral Clearance Endpoint	
Responder	Non-Responder
Subject with no evidence of HPV-16 or HPV-18 in vulvar tissue at evaluation AND Subject who did not receive any non-study related treatment for vulvar HSIL	Subject with evidence of HPV-16 or HPV-18 in vulvar tissue at evaluation OR Subject who received non-study related treatment for vulvar HSIL

Table 6: Definition of Responder and Non-responder for Complete HSIL Regression Endpoint	
Responder	Non-Responder
Subject with no histologic evidence of vulvar HSIL, LSIL (VIN1), or condyloma AND Subject who did not receive any non-study related treatment for vulvar HSIL	Subject with histologic evidence of vulvar HSIL, LSIL (VIN1), or condyloma at evaluation OR Subject who received non-study related treatment for vulvar HSIL

Table 7: Definition of Responder and Non-responder for Disease Non-Progression Endpoint	
Responder	Non-Responder
Subject with no histologic evidence of a worsening vulvar condition to vulvar cancer at Week 48 relative to baseline  AND  Subject who did not receive any non-study related treatment for vulvar HSIL	Subject with histologic evidence of worsening of vulvar condition to vulvar cancer at Week 48 relative to baseline  OR  Subject who received non-study related treatment for vulvar HSIL

Table 8: Definition of Responder and Non-responder for HSIL Regression or Viral Clearance Endpoint	
Responder	Non-Responder
Subject with no histologic evidence of vulvar HSIL  OR  Subject with no evidence of HPV-16 or HPV-18 in vulvar tissue at evaluation  AND  Subject who did not receive any non-study related treatment for vulvar HSIL	Subject with histologic evidence of vulvar HSIL or vulvar carcinoma at evaluation  AND  Subject with evidence of HPV-16 or HPV-18 in vulvar tissue at evaluation  OR  Subject who received non-study related treatment for vulvar HSIL

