## 8.9 EFFICACY ANALYSIS

The true treatment effect on the primary endpoint is  $p$ , where  $p$  denotes the true population probability of the primary endpoint for each arm. The primary hypothesis of superiority is:

$H_0: p \leq 0.02$  vs.  $H_1: p > 0.02$ , for each treatment study group separately.

A p-value for these hypothesis tests and corresponding 95% confidence intervals will be computed based on the exact method of Clopper-Pearson. Superiority will be concluded if the one-sided p-value is  $< 0.025$  and the corresponding lower bound of the 95% CI exceeds 0.02.

The secondary efficacy binary endpoints will be analyzed in the same manner as the primary hypothesis, but without the hypothesis test p-values. All of the efficacy binary endpoints will be analyzed in two ways: a) based on qualifying and new lesions, and b) based on all lesions. Also, the Week 74 binary endpoint will be analyzed overall, and according to four or five doses received, and the Week 96 binary endpoint will be analyzed overall, and according to four, five, or six doses received.

For the analyses, the efficacy time frame is defined by any time starting from 14 days prior to the -specified visit week.

The anatomic extent endpoint will be analyzed by calculating the mean percent change and associated 95% t-distribution based confidence interval. The percentage of subjects with no clinically significant lesion resolution (reduction in lesion size of 25% or less), partial lesion resolution (26-99% reduction), and complete reduction (100% reduction) will be summarized with point estimates and associated exact Clopper-Pearson 95% confidence intervals.

An exploratory analysis will examine clearance outside of the vulva. This will be analyzed in the same manner as vulvar clearance.

An exploratory analysis will examine the relationship between the primary efficacy endpoint and a) miRNA results, b) vulvoscopy results, and c) HPV results. Relationships will be examined with contingency tables and/or logistic regression models which model the primary endpoint versus these results and treatment group as regressor variables.

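### The exploratory lesion-area endpoint (Weeks 74/96) has no rule for women operated on from Week 48, so an excised lesion could count as resolution on VGX-3100

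*Protocol*

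**What the plan says.** All references are to Protocol Version 5.0.

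- **Endpoints.** Secondary endpoint 6 is the percent reduction in area of the "qualifying lesion(s) at Week 48 compared to baseline". Exploratory endpoint 1 is the same measure for the "qualifying lesion(s) at Week 74 and/or Week 96 compared to baseline", restricted in section 2.3 to analysis "in subjects without a complete resolution at Week 48". In both, complete resolution means only that no lesion can be seen.
- **Analysis.** Section 8.9: "The anatomic extent endpoint will be analyzed by calculating the mean percent change and associated 95% t-distribution based confidence interval". It adds three categories of reduction with exact intervals. Section 8.13 uses reported values without imputation. The mITT definition in 8.4 requires one dose and an available endpoint.
- **Surgery.** Section 6.2.10 allows wide excision at Week 48 at the Investigator's discretion. Where HSIL remains at Week 48 and the lesion has not grown, section 3.2 offers a fifth dose; alternatively, "the Investigator may choose to treat the subject with surgical or standard treatment, and the subject will continue on study without further biopsy". Women with worsening disease (Subgroup E) have surgery and continue with vulvoscopy but without biopsy or study treatment.
- **Measurement afterwards.** Footnote k of the Schedule of Events requires photographs of qualifying lesions at every vulvoscopy. Sections 3.2 and 6.2.12 schedule area measurement at Week 74. None of these exempts operated women.
- **Parallel endpoints.** The responder columns of Table 3 (3.2.1) and Tables 4-8 (3.2.2) all require: "Subject who did not receive any non-study related treatment for vulvar HSIL". Exploratory endpoint 5, on non-vulvar clearance, is likewise limited to clearance without surgery. There is no such table or condition for lesion area.

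**The concern.** For the binary response endpoints the protocol recognises that a lesion removed by other means is not a response to VGX-3100. For lesion area it does not, yet area is the measure that excision changes most directly. Exploratory endpoint 1 is also measured after the surgery decision, in a group that overlaps the women likely to be operated on. The analysis could therefore credit the surgeon's result to the vaccine, in both the mean percent change and the complete-resolution rate. A reader would see long-term area results that disagree with the histology and HPV results for the same women, with no stated reason.

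**Working it through.** The plan gives no expected area reduction, no surgery rate and no precision target for this endpoint, so there is no figure to reproduce. The sample-size statement in 8.3 concerns the primary endpoint and has no bearing here.

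**Step 1. Follow one operated woman through the text.** She has residual lesion and HSIL at Week 48 and is operated on after the result.

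| Question | Text | Consequence |
|---|---|---|
| Is she still on study? | 3.2: yes, without biopsy | Week 74 visit takes place |
| Is she photographed and measured? | Footnote k, 3.2, 6.2.12: yes, no exception | An area value can exist |
| Is she in the population? | 2.3: not completely resolved at Week 48 | Yes |
| How is she classed? | 2.3: complete if nothing is visible | Complete, 100% reduction |
| Is the value set aside? | 8.9, 8.13: no such rule | Used as reported |

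**Step 2. The other reading.** The endpoint specifies pre-biopsy images, and she has no further biopsy. She could be held to have no evaluable image and so fall outside the mITT set for this endpoint. Women with persistent or worsening disease would then leave the denominator.

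**Step 3. Which measurements are reached.** Secondary endpoint 6 is measured at Week 48 before biopsy or excision (6.2.10), so Week 52 surgery cannot change it. For women finishing at Week 78, no area is measured after Week 74, so only treatment before the Week 74 image matters. For the few with a Week 96 measurement, treatment after Week 74 matters too.

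**Step 4. Size, on assumed numbers only.** Take N = 18 women not completely resolved at Week 48. Let k be operated on before Week 74, each then showing a 100% reduction. Let the others have a mean reduction of 20% and about 10% complete resolution, rounded to c whole women.

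- Literal complete-resolution rate = (c + k)/18
- Rate with operated women as not resolved = c/18
- Rate with operated women dropped = c/(18 − k)
- Literal mean reduction = [20(18 − k) + 100k]/18

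| k | c | Literal | Not resolved | Dropped | Literal mean |
|---|---|---|---|---|---|
| 0 | 2 | 2/18 (11%) | 2/18 (11%) | 2/18 (11%) | 20.0% |
| 2 | 2 | 4/18 (22%) | 2/18 (11%) | 2/16 (13%) | 28.9% |
| 4 | 1 | 5/18 (28%) | 1/18 (6%) | 1/14 (7%) | 37.8% |
| 6 | 1 | 7/18 (39%) | 1/18 (6%) | 1/12 (8%) | 46.7% |
| 9 | 1 | 10/18 (56%) | 1/18 (6%) | 1/9 (11%) | 60.0% |

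Each operated woman adds 1/18 = 5.6 points to the complete-resolution rate compared with counting her as not resolved. She adds (100 − 20)/18 = 4.4 points to the mean if her own reduction before surgery was 20%. If it was 0%, she adds 100/18 = 5.6 points, and more if her lesion had grown.

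**Step 5. Category limits.** Section 2.2 has "no clinically significant lesion resolution (reduction in lesion size of 0-25" percent as its lowest class, then above 25% and below 100%, then no visible lesion. Section 8.9 has 25% or less, then "partial lesion resolution (26-99% reduction), and complete reduction (100% reduction". Read together, every value has a class: 8.9 takes increases into its lowest class, and 2.2 places 25.5% or 99.5% in the partial class.

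**The case against.** The strongest reply is that the protocol is silent rather than wrong. A reader might infer that it scores excised lesions as complete resolution, but no passage says so. The pre-biopsy wording supports treating operated women as unevaluable, and a statistical analysis plan that is not shown could settle the matter. This stands as a limit on the claim. It does not remove the point. Section 3.2.2 sets responder definitions for secondary and exploratory endpoints, and 8.9 fixes the area estimator and classes. As they stand, those definitions give a biased result on one reading and selective loss on the other.

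Three further inferences go too far:

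- **That the secondary area endpoint is compromised.** It is measured at Week 48 before biopsy. Only narrow routes reach it: an unscheduled excision for suspected progression before Week 48 (6.13), or a late image accepted because the 8.9 time frame has a start but no stated end.
- **That the endpoint 1 population is exactly the group open to surgery.** The population is defined by visible area, whereas the Subgroup C/D option depends on HSIL at histology. A woman may have residual acetowhite area without HSIL, or HSIL in the biopsy that Table 2 requires when nothing is visible. The groups overlap only.
- **That the category limits leave values unclassified.** The limits in 8.9 are whole-number shorthand that 2.2 and 2.3 resolve.

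It is also fair to say that this is a descriptive, exploratory endpoint, and that the parallel histology and HPV endpoints already count operated women as failures.

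**Conclusion.** The point holds for exploratory endpoint 1. It lacks the treatment condition given to every binary endpoint in Tables 3-8. On its literal definition, a lesion excised before the Week 74 or 96 image would count as a 100% reduction and complete resolution on VGX-3100. The alternative reading drops women with persistent or worsening disease.

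The size is unknown because the documents give no surgery rate. The 5.6 and 4.4 points per operated woman rest on an assumed 18 women and an assumed 20% mean reduction. The 20% is not an unbiased reference, since operated women may differ from the rest. The primary endpoint is not touched, and neither is the Week 48 area result by Week 52 surgery. The long-term area results would need care in reading; it does not follow that efficacy results after Week 48 as a whole are uninterpretable.

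**What to change.** Add to 8.9, with a cross-reference from endpoint 1 in the synopsis and 2.3:

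*If lesion area is measured after excision of, or any non-study treatment for, vulvar HSIL, the subject is placed in the lowest resolution category and stays in the denominator. The mean percent change uses her last area measured before that treatment. A sensitivity analysis excludes these subjects.*

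Excision needs to be named. Wide excision at Week 48 is itself a protocol procedure, so the non-study wording of Tables 4-8 might not be taken to cover it. The rule should apply at any visit, which also closes the narrow routes to the Week 48 endpoint. Using the last pre-treatment area is a rule of attribution, not an estimate of what would have happened without surgery. Excluding operated women conditions on a decision taken after baseline, so it belongs in the sensitivity analysis only.

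As an editorial matter, align the 8.9 classes with 2.2 and 2.3: 25% or less including increases, above 25% to below 100%, and 100%.

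The cost is a few sentences. Medications and procedures during the study are already recorded under 6.14. No visit, procedure, clinical rule or sample size changes.

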## **4. SELECTION OF SUBJECTS**

### **4.1 INCLUSION CRITERIA**

Each subject must meet all of the following criteria to be enrolled in the study:

1. Must understand, agree and be able to comply with the requirements of the protocol. Subjects must be willing and able to provide voluntary consent to participate and sign a Consent Form prior to study-related activities;
2. Women aged 18 and above;
3. Vulvar infection with HPV types 16 and/or 18 confirmed by screening biopsy;
4. Vulvar tissue specimen/blocks must be collected within 10 weeks prior to anticipated date of first dose of study drug and have confirmed histologically confirmed vulvar HSIL by the Pathology Adjudication Committee at screening;

5. Must be judged by the Investigator to be an appropriate candidate for the protocol-specified procedure (i.e. excision or biopsy) required at Week 48;
6. Must have vulvar HSIL that is accessible for sampling by biopsy instrument and of adequate size to ensure that a visible lesion remains after an approximately 4 mm screening biopsy;
7. Must have vulvar HSIL that can be completely demarcated for area measurement;
8. Must meet one of the following criteria with respect to their reproductive capacity:
  - a. Is post-menopausal as defined by spontaneous amenorrhea for more than 12 months or spontaneous amenorrhea for 6-12 months with FSH level >40 mIU/mL;
  - b. Is surgically sterile due to absence of ovaries or due to a bilateral tubal ligation/occlusion performed more than 3 months prior to screening;
  - c. Women of Child Bearing Potential (WOCBP) are willing to use a contraceptive method with failure rate of less than 1% per year when used consistently and correctly from screening until 6 months following the last dose of investigational product. Acceptable methods are the following:
    - i. Hormonal contraception: either combined or progestin-alone including oral contraceptives, injectable, implants, vaginal ring, or percutaneous patches. Hormonal contraceptives must not be used in subjects with a history of hypercoagulability (e.g., deep vein thrombosis, pulmonary embolism);
    - ii. Abstinence from penile-vaginal intercourse when this is the subject's preferred and usual lifestyle;
    - iii. Intrauterine device or intrauterine system;
    - iv. Male partner sterilization at least 6 months prior to the female subject's entry into the study, and this male is the sole partner for that subject.

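### Section 8.9 models the primary composite endpoint against HPV results where exploratory objective 6 names histologic regression, so Week 48 tissue HPV is tested against an endpoint that contains it

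*Protocol*

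**What the plan says.** All references are to Version 5.0 of the protocol.

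Section 8.9 sets the association analysis: "An exploratory analysis will examine the relationship between the primary efficacy endpoint and a) miRNA results, b) vulvoscopy results, and c) HPV results". The method follows: "Relationships will be examined with contingency tables and/or logistic regression models which model the primary endpoint versus these results and treatment group".

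Exploratory objective 6 in Section 2.3, repeated in the synopsis, has a different outcome: "Describe association of microRNA (miRNA) profile, previous vulvoscopy, and HPV testing results with Week 48 histologic regression". Its endpoint lists the data: "Vulvoscopy, HPV test results (vulvar swab and vulvar tissue) and miRNA profile (Day 0, Week 15 and 48) in conjunction with histologic regression".

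Under Table 3 in Section 3.2.1, HPV-16/18 found in vulvar tissue at evaluation is by itself enough for non-response on the primary endpoint. Table 4 in Section 3.2.2 defines response for HSIL regression from histology and the absence of non-study treatment, with no HPV condition.

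On clearance outside the vulva, Section 8.9 says: "This will be analyzed in the same manner as vulvar clearance". The vulvar rule in Table 5 rests on "Subject with no evidence of HPV-16 or HPV-18 in vulvar tissue at evaluation", together with no non-study treatment. A synopsis footnote equates clearance with an undetectable PCR result. Exploratory endpoint 5 counts women whose non-vulvar HPV-16/18 has cleared by Week 48 relative to baseline.

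**The concern.** Two things look wrong.

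First, 8.9 and objective 6 name different outcomes for the same three sets of predictors, and nothing in the protocol reconciles them. For Week 48 tissue HPV-16/18 the outcome chosen in 8.9 already contains the predictor. An analyst following 8.9 would get a very large association that restates the endpoint definition. With only a handful of responders expected, it could be mistaken for a biomarker finding.

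Second, the vulvar clearance rule needs no baseline condition because every woman enters with "Vulvar infection with HPV types 16 and/or 18 confirmed by screening biopsy". No eligibility criterion requires HPV-16/18 at the cervix, oropharynx, vagina or anus. If the vulvar rule is carried over unchanged, a woman who never had HPV-16/18 at a site could be counted as having cleared it there. The inflated rate could be taken as support for the systemic clearance that Section 1.1.17 puts forward as a potential benefit.

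**Working it through.** The protocol gives no figure for either analysis, so there is nothing to reproduce. The check is of the definitions, with illustrations on assumed counts.

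**Association analysis**

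1. Vulvar tissue HPV is sampled at Screening and at Weeks 48, 74 and 96 (Section 3.5). The last two follow the outcome. At Screening a yes/no HPV-16/18 flag is positive for everyone. That leaves Week 48 as the only tissue result up to the outcome at which this flag can vary.

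2. Cross-classify Week 48 tissue HPV-16/18 against the primary endpoint. Let a and b be responders and non-responders among tissue-negative women, and c and d the same among tissue-positive women. Table 3 forces c = 0, so the odds ratio (a × d)/(b × c) is infinite. Tissue-negative women with residual HSIL are still non-responders, so b is usually above zero. The pattern is then quasi-complete separation: one empty cell.

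3. Scale, from the Section 8.3 assumptions: evaluable women are 24 × 0.90 = 21.6 and 12 × 0.90 = 10.8. Expected responders are 21.6 × 0.20 + 10.8 × 0.28 = 4.3 + 3.0 = 7.3. The second arm was closed to enrolment by Version 3.0 and its final size is not stated, so 7 is a planning figure.

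4. Illustrations, with the number of tissue-negative women assumed (two-sided Fisher exact test):

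| Evaluable | Responders | Tissue-negative (assumed) | Table [a, b], [c, d] | p |
|---|---|---|---|---|
| 22 | 4 | 6 | [4, 2], [0, 16] | 0.002 |
| 22 | 4 | 8 | [4, 4], [0, 14] | 0.010 |
| 22 | 4 | 12 | [4, 8], [0, 10] | 0.096 |
| 32 | 7 | 14 | [7, 7], [0, 18] | 0.001 |

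For example, the second row is C(8,4)/C(22,4) = 70/7,315 = 0.0096. A maximum-likelihood logistic fit to the last row did not converge (coefficient −25.8, standard error about 92,000).

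5. With Table 4 regression as the outcome, a tissue-positive woman whose histology has regressed is a responder. The empty cell is no longer forced, and the association becomes a real question.

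**Non-vulvar clearance**

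Let π be the share HPV-16/18 positive at a site on Day 0 and k the true clearance among them, with no new infection. If every woman in the modified intention-to-treat (mITT) population counts, the reported rate is (1 − π) + π × k. The protocol gives neither π nor k, so both are assumed:

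| π | k = 0 | k = 20% | Day 0 positives among 22 |
|---|---|---|---|
| 10% | 90% | 0.90 + 0.10 × 0.20 = 92% | 2.2 |
| 30% | 70% | 0.70 + 0.30 × 0.20 = 76% | 6.6 |
| 50% | 50% | 0.50 + 0.50 × 0.20 = 60% | 11 |

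Restricted to Day 0 positives, the rate equals k whatever π is.

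**The case against.** A reader might infer that every HPV result in this analysis is circular. The protocol does not support that. Endpoint 6 also names vulvar swabs, taken at Day 0 and Weeks 4, 12, 27 and 48, which are separate specimens and not part of the primary endpoint. Screening tissue is constant only as a yes/no HPV-16/18 flag. Genotype can vary, because eligibility accepts either type and Section 6.1.1 allows co-infection with others. Nor is the association perfect, since tissue-negative women may still have HSIL.

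A reader might also conclude that all Week 48 predictors should be barred. That goes too far. Week 48 miRNA is listed in endpoint 6, and Section 6.9 plans its comparison with Day 0. Once histologic regression is the outcome, even Week 48 tissue HPV is no longer circular.

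On non-vulvar clearance, the stronger reading is that women never positive at a site are counted as cleared, so that the result is fixed in advance. The text does not say so. Endpoint 5 speaks of clearance relative to baseline, which implies a positive baseline. Section 8.9 uses the same turn of phrase for the secondary endpoints, which keep their own responder definitions, so it may refer only to the statistical method. The mITT requirement that the endpoint be available could also be read to exclude never-positive women. Even under the unfavourable reading, the rate moves with true clearance. What stands is that the vulvar rule has no baseline condition and 8.9 supplies none.

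Finally, both analyses are descriptive and exploratory, in what Section 1.1.12 calls a pilot study. That bears on severity. It does not remove the contradiction over the outcome.

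**Conclusion.** The mismatch between 8.9 and objective 6 holds as written. For Week 48 tissue HPV-16/18 it produces an empty responder cell by definition, hence an infinite odds ratio and quasi-complete separation. This assumes that the HPV regressor is taken from lesions that also enter the endpoint. Section 8.9 analyses binary endpoints on two lesion sets, so mixing them could break the exact zero. The p-values above rest on assumed counts and show only that the artefact can look convincing. For the other predictors the defect is the wrong outcome alone.

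The non-vulvar point is conditional. If the vulvar rule were applied to the whole mITT population, clearance would be overstated, reading 90%, 70% or 50% with no true clearance at the assumed prevalences. The protocol leaves this open and does not require it.

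Neither point touches the primary test or the secondary endpoints. Severity is minor.

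**What to change.** In Section 8.9, replace the primary endpoint with Week 48 histologic regression, as defined in Table 4, as the outcome of the association analysis. The planned Week 48 miRNA and swab results can stay. If the sponsor prefers to keep the composite, leave out Week 48 tissue HPV-16/18 as a regressor. That removes the circularity, but objective 6 would then need rewording to match.

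Also in 8.9, align non-vulvar clearance with endpoint 5 by reporting it site by site among women HPV-16/18 positive at that site on Day 0.

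The cost is two sentences. No new samples are needed, because Section 3.5 already schedules all four non-vulvar sites at Day 0 and Week 48. Denominators for non-vulvar clearance shrink, to roughly 2 to 11 of 22 women at Day 0 prevalences of 10% to 50%, so the intervals will be wide.
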